6.2 RATIONALE

Data about the efficacy of a combination of *Phyllanthus niruri* (Dukung Anak) and

Silybum marianum (Milk Thistle) in patients with NASH are still lacking. Therefore, this study was designed to evaluate both on a larger clinical scale.

7 STUDY OBJECTIVES

7.1 PRIMARY

- To explore the anti-oxidant activity of Heptex as assessed by improvement in serum aspartate aminotransferase (AST) and alanine aminotransferase (ALT) levels in patients with apparent risk factors of NASH.

7.2 SECONDARY

- To explore the optimum dose that is safe in patients with apparent risk factors of NASH giving the most significant effect among two different doses of Heptex.
- To explore the hepatoprotective effect of Heptex as assessed by the change in Fibrosis score.
- To explore the hepatoprotective effect of Heptex as assessed by the occurrence of hepatic complications.

8 STUDY DESIGN

8.1 DESCRIPTION OF THE STUDY DESIGN

This is a phase II, randomized, double blind placebo-controlled, three-arm, parallel-group, interventional clinical trial evaluating anti-oxidant activity of Heptex; a herbal medicinal product of Aerial Parts of *Phyllanthus niruri* (Dukung Anak) and Fruits of *Silybum marianum* (Milk Thistle).

Study duration: 12 weeks of recruitment and 36 weeks of treatment. This period will include 2 washout periods (at Week 13 & Week 25).

Sample Size: 47 subjects per arm, 141 in total.

Participants in trial will be patients between 18 and 65 years consenting to participate in this study, who have elevated liver enzymes^[34], controlled attenuation parameter (CAP)-confirmed hepatic steatosis, and Fib score of F1 and F2 assessed by the FibroScan liver stiffness measurement.

FibroScan will be done for all patients at screening visit and those with F1 and F2 will be considered for inclusion in the study. FibroScan will be repeated for all patients after 6 months and at the end of treatment duration and results will be compared.

Screening of patients will be continued for about 12 weeks. Eligible patients will be randomized in a 1:1:1 allocation ratio, into one of the three treatment groups, to receive either placebo or one of the two doses of Heptex. Randomization will be done using interactive response technology.

8.2 DURATION OF STUDY PARTICIPATION

This phase II study will last for 36 weeks in addition to a screening period, and it will include 2 washout periods (at Week 13 & Week 25). A total of 6 visits will be performed as shown in the table below;

Visit 1	Visit 2	Visit 3	Visit 4		Visit 5		Visit 6
Screening (12 weeks)	Baseline	Follow up	Follow up	Washout period (Week 13)	Follow up	Washout period (Week 25)	Follow up (EOS)
	Week 0	Week 8	Week 12		Week 24		Week 36

8.3 ESTIMATED STUDY DATES

- Protocol Planned Date: October 2018
- First Patient In (FPI): December 2018
- Last Patient In (LPI): March 2019
- Last Patient Out (LPO): December 2019
- Estimated enrollment duration: 3 Months
- Estimate treatment duration: 9 Months
- Database lock planned date: January 2020
- Estimated Report date: February 2020

8.4 DATA TO BE COLLECTED AT DIFFERENT STUDY INTERVALS

Screening visit:

During screening visit, data on informed consent process, inclusion and exclusion criteria, demographics, medical and surgical history, concomitant medications, physical examination, vital signs, FibroScan liver stiffness measurement (KPa), abdominal ultrasound, controlled attenuation parameter (CAP), lab tests (serum pregnancy test for females, PCR; HCV RNA, HAV IgM antibody test, HBsAg test, alpha fetoprotein, CBC, sodium, potassium, serum fibrinogen, albumin, bilirubin, prothrombin time, PTT, INR, ALT, AST, kidney function tests, lipid profile, and HbA1c) will be collected. Then Fib-4 score will be calculated.

Baseline (week 0):

At baseline visit, data on concomitant medications, physical examination and vital signs will be collected. Then occurrence of adverse events and serious adverse events

including hepatic complications will be collected. Data on the dispensed drug will be recorded.

Week 8 and week 12:

At week 8 and week 12, data on concomitant medications, physical examination, vital signs, controlled attenuation parameter (CAP), lab tests (serum pregnancy test for females, CBC, serum fibrinogen, albumin, bilirubin, prothrombin time, PTT, INR, ALT and AST) will be collected. Then Fib-4 score will be calculated and occurrence of adverse events and serious adverse events including hepatic complications will be collected. The drug accountability for the dispensed drug will be recorded.

Week 24:

At week 24, data on concomitant medications, physical examination, vital signs, FibroScan liver stiffness measurement (KPa), controlled attenuation parameter (CAP), lab tests (serum pregnancy test for females, CBC, sodium, potassium, serum fibrinogen, albumin, bilirubin, prothrombin time, PTT, INR, ALT, AST, kidney function tests, lipid profile and HbA1c) will be collected. Then Fib-4 score will be calculated and occurrence of adverse events and serious adverse events including hepatic complications will be collected. The drug accountability for the dispensed drug will be recorded.

Week 36:

At week 36, data on concomitant medications, physical examination, vital signs, FibroScan liver stiffness measurement (KPa), controlled attenuation parameter (CAP), lab tests (serum pregnancy test for females, CBC, sodium, potassium, serum Fibrinogen, albumin, bilirubin, prothrombin time, PTT, INR, ALT, AST, kidney function tests, lipid profile and HbA1c) will be collected. Then Fib-4 score will be calculated and occurrence of adverse events and serious adverse events including hepatic complications will be collected. Study completion form will be filled.

9 SELECTION OF PATIENTS

9.1 SAMPLE SIZE

It is planned to recruit 141 patients (47 patients per arm), in 2 centers in Egypt.

9.2 INCLUSION CRITERIA

- 1) Male or female aged between 18 and 65 years.
- 2) Both male and female patients who have childbearing potential must agree to practice an acceptable method of birth control during the study and for at least 6 months after the cessation of treatment; such contraceptive methods must include at least one barrier method.
- 3) Controlled Attenuated Parameter (CAP)-confirmed hepatic steatosis.
- 4) Patients with elevated Liver enzymes (ALT and/or AST) ^[34].
- 5) Liver fibrosis stage F1-F2 as diagnosed by the FibroScan liver stiffness measurement of 5-10 kPa.
- 6) liver condition according the following criteria;
 - Serum albumin > 3 g/dl
 - INR < 2
 - No ascites on ultrasound
 - No documented or suspected hepatic encephalopathy
- 7) Willing to stop any other liver support and hepatoprotective medications throughout study duration.
- 8) Able and willing to provide written informed consent.
- 9) Able and willing to complete all study visits and procedures, including compliance with the requirements and restrictions listed in the consent form.

9.3 EXCLUSION CRITERIA

- 1) Pregnant or lactating women.
- 2) Patients with BMI > 40 Kg/m² or BMI < 18.5 Kg/m².

- 3) Serum creatinine > 1.5 x ULN OR creatinine clearance (GFR) < 60 mL/minute.
- 4) Platelet count < 75,000/mm³.
- 5) Uncontrolled diabetes mellitus as evident by HbA1c ≥ 8.5%.
- 6) Patients who are currently receiving Thiazolidinediones.
- 7) Patients with ischemic heart disease (IHD).
- 8) History of parenteral nutrition.
- 9) History of liver transplant.
- 10) Viral hepatitis, drug-induced liver injury, metabolic liver disease or autoimmune liver disease.
- 11) Liver cancer or serum alpha-fetoprotein (AFP) >100ng/ml. Patients with an AFP between 50 and 100ng/ml may be included as long as a liver ultrasound within 3 months of screening, or at screening, shows no evidence of potential hepatocellular cancer.
- 12) Use of drugs known to induce steatosis (valproate, amiodarone or prednisone) or to affect body weight and carbohydrate metabolism.
- 13) Use of drugs known to alter liver enzymes.
- 14) Allergy or allergic history to any of the drug components.
- 15) History of alcohol abuse as assessed by the investigator within the past 2 years, or an alcohol use pattern that may interfere with the patient's study compliance. Patients must have abstained from alcohol for at least 6 months prior to study start.
- 16) Patients with history of clinically-significant illness or any other major medical disorder that may interfere with subject treatment, assessment, or compliance with the protocol.
- 17) Receipt of an investigational drug within 6 months prior to screening, or active enrolment in another investigational medication or device trial.
- 18) Patients with any chronic illness or prior treatment which in the opinion of the investigator should preclude participation in the trial.
- 19) Inability to understand and cooperate with the investigators or to give valid consent.

10 TREATMENT OF TRIAL PARTICIPANTS

10.1 RANDOMIZATION

Before randomization, fulfillment of the inclusion/exclusion criteria should be assured and the signed informed consent obtained. After that, eligible patients will be randomized in a 1:1:1 allocation ratio, into one of the three treatment groups, to receive either placebo or one of the two doses of Heptex. Randomization will be done using interactive response technology.

Control Arm 1:

Placebo (Rice bran) in 2 capsules size 1, administered PO TID on empty stomach with plenty of water.

Experimental Arm 2:

The contents of one capsule of Heptex is equally distributed and inserted into 2 capsules size 1, administered PO TID on empty stomach with plenty of water.

Experimental Arm 3:

The contents of two capsules of Heptex is equally distributed and inserted into 2 capsules size 1, administered PO TID on empty stomach with plenty of water.

10.2 INVESTIGATIONAL PRODUCT

Heptex Capsule (Size 1) consists of the following;

Dukung Anak is a Powdered Extract 200 mg (from Aerial Parts of *Phyllanthus niruri*),

Milk Thistle is a Powdered Extract 100 mg (from Fruits of *Silybum marianum*).

Sponsor will provide the study treatment for the patients during the whole treatment duration according to regulation of Local Health Authorities involved in the product supply. Clinical Supplies will be pre-prepared for a sufficient number of patients entering double-blind treatment.

10.3 LABELLING AND PACKAGING

Investigational products will be packed in HDPE (High-density polyethylene) white bottles. Bottles will be packed in white carton boxes. A label will identify the patient's initials, patient stratification, randomization number, site number, visit date, visit number, batch number, no. of capsules, sponsor's name, dosage form, expiry date,

storage instructions and instructions to keep out of the reach of children in addition to a statement that this medication is for clinical trial use only. Investigational products will be stored at ambient temperature (not to exceed 30°C). During each study visit (from visit 2 to visit 6), each patient will receive a number of bottles containing the amount of medications sufficient for 8 or 12 weeks (according to visit interval).

10.4 MODE OF ADMINISTRATION:

Each patient will take 2 capsules size 1 of the study medication (either Placebo or Heptex) orally (PO) three times daily (TID) on empty stomach (15 min before meals or 1 hour after meals) with plenty of water (240 ml water, or full glass of water) for 9 months. The Placebo and Heptex capsules will be identical in physical appearance and mode of administration.

10.5 ACCOUNTABILITY OF STUDY TREATMENT:

The investigator or officially delegated pharmacist will be responsible for recording the receipt, administration and return of all drug supplies, and for ensuring the supervision of the storage and allocation of these supplies.

It is essential that the patients are able to accurately account for all supplies issued to them (i.e. Patient Event Log records of study drug taken should match drug supplies returned).

The investigator may withdraw any patient from the study if missing drug supplies cannot be satisfactorily accounted for, or if drug accountability records are consistently inaccurate, e.g. a patient may be discontinued if he has been cautioned to account correctly for medication issued and on a subsequent visit has failed to record two or more doses taken.

Any quality issue noticed with the receipt or use of an Investigational Product (deficient IP in condition, appearance, pertaining documentation, labeling, expiry date, etc.) should be promptly notified to the Sponsor, who will initiate a complaint procedure.

Under no circumstances will the Investigator supply Investigational Product to a third party, allow the Investigational Product to be used other than as directed by this Clinical Trial Protocol, or dispose of Investigational Product in any other manners.

11 CONCOMITANT MEDICATIONS

Throughout the study, investigators may prescribe any concomitant medications or treatments deemed necessary to provide adequate supportive care except other liver support, hepatoprotective medications and any medications prohibited as per the eligibility criteria. If these are required, the participant will be withdrawn. Any medication, other than the study medication taken during the study will be recorded in the CRF.

Any medication or vaccine (including over-the-counter or prescription medicines, vitamins and/or herbal supplements) that the subject is receiving during participation in the study must be recorded in the electronic case report form. The investigator should review all concomitant medications for any potential interactions. During the Post-Treatment Period, all medications will be collected.

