16.2 ANALYSIS POPULATIONS

The obtained clinical data will be analyzed on an intention-to-treat basis. Primary analysis will be done by intention-to-treat including all eligible enrolled patients with at least one treatment dose and post first dose assessment (ALT & AST) attending any post treatment visit and efficacy variables will be analyzed using the last-observation-carried-forward convention (LOCF).

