18 DISCONTINUATION/ WITHDRAWAL OF PARTICIPANTS FROM STUDY

Each participant has the right to withdraw from the study at any time. In addition, the investigator may discontinue a participant from the study at any time if the investigator considers it necessary for any reason including:

- 1) Ineligibility (either arising during the study or retrospective having been overlooked at screening)
- 2) Significant protocol deviation
- 3) Significant non-compliance with treatment regimen or study requirements
- 4) Disease progression which requires discontinuation of the study medication or results in inability to continue to comply with study procedures
- 5) Consent withdrawn.
- 6) Lost to follow up

The reason for withdrawal will be recorded in the CRF.

If the participant is withdrawn due to an adverse event, the investigator will arrange for follow-up visits or telephone calls until the adverse event has resolved or stabilized.

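### The protocol does not separate stopping study drug from leaving the study and provides for no ALT/AST after withdrawal, so its intention-to-treat analysis is a modified one that relies on carried-forward values

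*Protocol*

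**What the plan says.** Three sections of the protocol govern withdrawal.

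- **Section 11** lets investigators prescribe supportive care but not liver-support drugs, hepatoprotective drugs or anything barred by the eligibility criteria. It then states: "If these are required, the participant will be withdrawn". This is mandatory. It does not say whether the withdrawal is from drug or from the study.
- **Section 10.5** is discretionary: "The investigator may withdraw any patient from the study if missing drug supplies cannot be satisfactorily accounted for". Its example is a patient already cautioned about accounting for medication who "on a subsequent visit has failed to record two or more doses taken".
- **Section 18** is also discretionary: "the investigator may discontinue a participant from the study at any time if the investigator considers it necessary for any reason including". The list that follows includes significant deviation, "Significant non-compliance with treatment regimen or study requirements", and disease progression that requires study medication to be stopped.

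On follow-up, section 18 says only: "If the participant is withdrawn due to an adverse event, the investigator will arrange for follow-up visits or telephone calls". This lasts until the event has resolved or stabilised, and no ALT/AST is specified. The assessment schedule in section 2 has six visits and no early-termination or off-drug visit. Section 11 mentions a post-treatment period, but the schedule contains none.

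On analysis, section 16.2 opens with "The obtained clinical data will be analyzed on an intention-to-treat basis" and continues "Primary analysis will be done by intention-to-treat including all eligible enrolled patients with at least one treatment dose". It adds that an ALT/AST measured after the first dose is needed and that gaps are filled by last observation carried forward (LOCF). Section 16.4.2 runs the same primary comparisons on patients free of protocol violations (relative change) or of protocol deviations (normalisation).

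**The concern.** An intention-to-treat comparison needs the outcome of patients who stop treatment, not only of those who stay on it. Here the withdrawal rules take patients out and nothing tells sites to go on measuring them.

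Several of the reasons for leaving lie close to the outcome: needing a hepatoprotective drug, progressing, or not complying. In a trial of placebo against two doses, the frequency of such exits may differ by arm. If it does, the last value before withdrawal is not a neutral stand-in for week 36, and the comparison loses part of the protection that randomisation gives.

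The secondary endpoint of hepatic complications is exposed in the same way. A patient withdrawn for progression or for a prohibited drug, and not for an adverse event, has no scheduled contact afterwards.

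A statistical analysis plan cannot repair this, because it cannot create measurements that the protocol does not ask sites to take.

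**Working it through.** **1. Is collection after withdrawal provided for?**

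| Route out | Force | From the study? | ALT/AST afterwards |
|---|---|---|---|
| Section 11, barred drug required | mandatory | not stated | none provided for |
| Section 10.5, accountability | discretionary | yes | none provided for |
| Section 18, deviation, non-compliance, progression | discretionary | yes | none provided for |
| Section 18, adverse event | discretionary | yes | event follow-up only |

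Section 18 makes stopping study medication for progression a reason for leaving the study, so there the two are joined in the text itself.

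**2. What does section 16.2 then use?** After screening, ALT/AST are scheduled at weeks 8, 12, 24 and 36 (section 2).

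| Withdrawn | Last scheduled value | Carried forward to week 36 over |
|---|---|---|
| before week 8 | none post-dose | patient is outside the 16.2 set |
| after week 8, before week 12 | week 8 | 36 − 8 = 28 weeks |
| after week 12, before week 24 | week 12 | 36 − 12 = 24 weeks |
| after week 24, before week 36 | week 24 | 36 − 24 = 12 weeks |

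A patient withdrawn at week 20 because liver support is needed would thus be represented by an on-drug value from week 12, and could count as normal at end of treatment. So the 16.2 analysis can be computed, but it is a modified intention-to-treat analysis.

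**3. Would better collection be enough?** No. Under section 16.4.2 protocol violators are excluded from the same primary analysis, whatever data exist for them. Sections 16.2 and 16.4.2 contradict each other on the population.

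**4. Numbers.** The inputs from section 16.1 are an effect size of 0.63, power 80%, alpha 5%, 43 evaluable per arm, 10% dropout, and 47 per arm (141 in total).

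- *Plan's own figure.* A Mann–Whitney calculation (noncentral t, asymptotic relative efficiency 3/π) gives 43 per arm for a two-sided 5% test, with 80.5% power. The one-sided 5% test as written gives 34. That mismatch is a separate matter. For dropout, 43 × 1.10 = 47.3, which agrees with 47.
- *Patients concerned, upper limit.* 0.10 × 141 = 14.1, about 14. This is all-cause dropout, so it is a ceiling at the planned rate and not an estimate for these rules.
- *Withdrawn patients add no week 36 value (assumed rates).* At 10%, 20% or 30%, 47 per arm leaves 42, 37 or 32. Two-sided power is then 79.6%, 74.2% or 67.8%.
- *Withdrawn patients are followed, but the effect is diluted (assumed).* A 10% dilution gives 0.63 × 0.90 = 0.567 and a 20% dilution gives 0.63 × 0.80 = 0.504. Two-sided power at 47 per arm is then 75.7% or 65.6%.

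These figures describe precision, not bias. Bias would need withdrawal rates by arm and reason, and the protocol gives none.

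**The case against.** Much can be said for the protocol, and several stronger readings that a reader might infer do not hold.

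- *Patients who deviate or misrecord doses are withdrawn.* Not automatically. Sections 10.5 and 18 say the investigator may do so, and section 18 asks for a significant deviation or significant non-compliance. The two-dose example applies only after a caution and a further failure at a later visit. Setting two doses against all doses over 36 weeks would use the wrong denominator, because the rule concerns records found deficient at one visit.
- *Week 36 values are never collected.* This is an inference from silence. Nothing forbids later ALT/AST, and section 11 does not itself say that the patient leaves the study. What stands is that no collection is provided for.
- *Intention-to-treat analysis is impossible.* It is not. Section 16.2 defines an analysis that can be run on anyone with one post-dose ALT/AST. What stands is that the label promises more than the data would support.
- *The normal-enzyme proportion could shift by up to 10 percentage points per arm.* That bound treats all planned dropout as caused by these rules. The 10% also covers consent withdrawal and loss to follow-up, which section 18 lists and which no change of wording would recover.

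The most serious counter-argument concerns the estimand. ALT/AST measured after a hepatoprotective drug is started partly reflect that drug, and in an exploratory phase II trial one may prefer not to rest the primary comparison on them. That is a fair choice, but it concerns use, not collection. Values that were collected can be left out of an analysis; values that were not collected cannot be put in. Since section 16.2 claims intention-to-treat, its own choice points to using them.

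**Conclusion.** The point holds in a limited form. Sections 10.5, 11 and 18 do not separate stopping drug from leaving the study, and no ALT/AST is provided for afterwards. The result is a modified intention-to-treat analysis that carries pre-withdrawal values forward by 12 to 28 weeks and omits patients who leave before any post-dose value. Section 16.4.2 contradicts it by excluding protocol violators altogether.

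The size of any bias cannot be stated from the protocol. At the planned all-cause dropout at most about 14 of 141 patients are concerned; the share due to these rules is unknown. That the missing values are informative is a judgement from the nature of the reasons, not something the document shows. The conclusion also assumes that sites read silence on later visits as meaning none.

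This should be put right in the protocol, but it does not by itself invalidate the trial.

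**What to change.** 1. In sections 10.5, 11 and 18, state that a patient who stops study drug, for any reason the protocol already gives, stays in the study and attends the remaining scheduled ALT/AST visits to week 36 unless consent is withdrawn. Record any prohibited medication started, with its date. The clinical reasons for stopping drug are not changed.
2. Reconcile section 16.2 with 16.4.2 so that the primary analysis keeps these patients in the arm to which they were randomised. Use the set without protocol violations as a sensitivity analysis. Without this step the extra data would be discarded.
3. Reconcile the post-treatment period named in section 11 with the visit schedule.

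The cost is protocol wording and visits that are already scheduled, for at most about 14 patients at the planned dropout. The planned sample size does not change. The statistical price is possible dilution by values after discontinuation, as illustrated above under assumed rates. Patients who withdraw consent or are lost to follow-up will still be missing.
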